### 12.6.2 Analysis Plans for Secondary Objectives

Any subject who receives at least one dose of treatment on this protocol is evaluable for toxicity. Toxicity rates will be summarized using frequency tables. Disease control rates will be analyzed based on the exact binomial test. Duration of response will be the time from the first documentation of response to the time of progression or death will be summarized using frequency tables. Progression free survival and overall survival curves will be based on the Kaplan-Meier method.

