| Comprehensive Metabolic Profile (CMP)                     | X               | X                                      |  | X                                       | X                                |                           | X   |
| Amylase and Lipase  | X               | X                                      |  |   |                                  |                           | X   |
| GGT and Magnesium level                                   | X               |  |  |   |                                  |                           | X   |
| PT/INR and aPTT   | X               |  |  |   |                                  |                           | X   |
| Thyroid Function (TSH, T4, free T3)           | X               | X                          |  |   |                                  |                           | X   |
| Pregnancy test (serum or urine) (WOCBP)       | X               |  |  |   |                                  |                           | X   |
| Hepatitis B and C and HIV                     | X               |  |  |   |                                  |                           |   |
| Urinalysis                                    | X               |  |  |   |                                  |                           | X   |
| DISEASE ASSESSMENT                                 |                 |  |  |   |                                  |                           |   |
| CT of chest                                   | X               | X                          |  | X                           | Every 3
months
(± 7 days)  |                           | X   |
| CT or MRI of abdomen and pelvis               | X               | X                          |  | X                           |                                  |                           | X   |
| Bone scan in subjects with bone metastases    | X               | X                          |  | X                           |                                  |                           | X   |
| TREATMENT EXPOSURE                                 |                 |  |  |   |                                  |                           |   |

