### 11.1 Definitions

#### 11.1.1 Adverse Event (AE)

An AE is any untoward medical occurrence whether or not considered related to the study drug that appears to change in intensity during the course of the study. The following are examples of AEs:

- Unintended or unfavorable sign or symptom
- A disease temporally associated with participation in the protocol
- An intercurrent illness or injury that impairs the well-being of the subject

Abnormal laboratory values or diagnostic test results constitute AEs only if they induce clinical signs or symptoms or require treatment or further diagnostic tests

Hospitalization for elective surgery or routine clinical procedures that are not the result of an AE (e.g., surgical insertion of central line) should not be recorded as an AE.

Disease progression should not be recorded as an AE, unless it is attributable to the study regimen by the site investigator.

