### 11.1.3 Adverse Events of Special Interest

An adverse event of special interest (AESI) is one of scientific and medical interest specific to understanding of the study drug(s) and may require close monitoring and rapid communication by the site investigator to the sponsor-investigator. An AESI may be serious or non-serious. The rapid reporting of AESIs allows ongoing surveillance of these events in order to characterize and understand them in association with the use of the study drug(s). If any AESI occurs in the course of the study, then the site investigators or other site personnel should report to Hoosier Cancer Research Network (HCRN) **within 1 business day** of becoming aware of the event.

HCRN will report to AstraZeneca **within 1 business day** of becoming aware of the event. AESIs for tremelimumab include, but are not limited to, events with a potential inflammatory or immune-mediated mechanism and that may require more frequent monitoring and/or interventions such as steroids, immunosuppressants, and/or hormone replacement therapy. These AESIs are being closely monitored in clinical studies with tremelimumab therapy.

An imAE is defined as an AE that is associated with drug exposure and is consistent with an immune-mediated mechanism of action and where there is no clear alternate etiology. Serologic, immunologic, and histologic (biopsy) data, as appropriate, should be used to support an imAE diagnosis. Appropriate efforts should be made to rule out neoplastic, infectious, metabolic, toxin, or other etiologic causes of the imAE. In the event of imAE or suspected imAE, the sponsor-investigator may request relevant clinical information (including images) for those subjects who demonstrate the event and may request the independent review by external experts based on the acquired clinical information.

If the site investigator has any questions with regards to an AE being an imAE, the site investigator should immediately contact the sponsor-investigator.

AESIs observed with tremelimumab include the following:

- Diarrhea/Colitis and intestinal perforation
- Pneumonitis/Interstitial Lung Disease (ILD)
- Hepatitis/transaminase increases
- Neuropathy / neuromuscular toxicity (e.g. Guillain-Barré, and myasthenia gravis)
- Endocrinopathy (ie, events of hypophysitis, adrenal insufficiency, and hyperthyroidism and hypothyroidism, Type I diabetes)
- Rash/Dermatitis
- Nephritis/Blood creatinine increases

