- Pancreatitis/ serum lipase and amylase increases
- Myocarditis
- Myositis/Polymyositis
- Other inflammatory responses that are rare / less frequent with a potential immune-mediated aetiology include, but are not limited to, pericarditis, sarcoidosis, uveitis and other events involving the eye, skin, haematological and rheumatological events.

In addition, infusion-related reactions and hypersensitivity/anaphylactic reactions with a different underlying pharmacological etiology are also considered AESIs. Further information on these risks (e.g. presenting symptoms) can be found in the current version of the tremelimumab Investigator's Brochure. More specific guidelines for their evaluation and treatment are described in detail in the Dosing Modification and Toxicity Management Guidelines (please see Appendix 1). These guidelines have been prepared by the Funder to assist the investigators in the exercise of his/her clinical judgment in treating these types of toxicities. These guidelines apply to AEs considered causally related to the study drug/study regimen by the reporting investigator)

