## 11.2 Reporting

### 11.2.1 Adverse Events

AEs will be recorded from time of signed informed consent until 30 days after discontinuation of study drug(s) or until a new anti-cancer treatment starts, whichever occurs first.

- AEs will be recorded regardless of whether or not they are considered related to the study drug(s).
- All AEs will be recorded in the subject's medical record and on the appropriate study specific eCRF form within the EDC system.
- AEs considered related to study drug(s) will be followed until resolution to  $\leq$  Grade 1 or baseline, deemed clinically insignificant, and/or until a new anti-cancer treatment starts, whichever occurs first.
- Asymptomatic laboratory abnormalities that do not require treatment will not be collected as adverse events.

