### 12.4 Assessment of Safety

The safety population will be defined as any patients that receive at least one dose of tremelimumab and will be used in the assessment of toxicity. Safety will be determined according to the NCI Common Terminology Criteria for Adverse Events (NCI CTCAE) v4.03. All subjects will be evaluable for adverse event evaluation from the time of their first dose of study treatment.

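### Laboratory-defined toxicity may be undercounted: Sections 11.1.1, 11.1.3 and 11.2.1 disagree on which abnormal values become adverse events, and no summary of the laboratory values themselves is planned

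*Combined protocol and SAP*

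**What the plan says.** **Analysis.** Section 12.4 defines the safety population as anyone given at least one dose and says "Safety will be determined according to the NCI Common Terminology Criteria for Adverse Events (NCI CTCAE) v4.03". Section 12.6.2 then says "Toxicity rates will be summarized using frequency tables". Section 12.7 adds a formal stopping rule on treatment-related Grade 3 or higher adverse events, with looks after 6, 12, 18 and 24 subjects. Section 13.2 sends the monitoring committee an adverse event summary and the stopping-rule data. No section plans a summary of laboratory values, whether by worst grade, shift or change from baseline.

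**What becomes an adverse event.** The definition in Section 11.1.1 reads "Abnormal laboratory values or diagnostic test results constitute AEs only if they induce clinical signs or symptoms or require treatment or further diagnostic tests". The collection rule in Section 11.2.1 reads "Asymptomatic laboratory abnormalities that do not require treatment will not be collected as adverse events". Section 11.1.3 lists among the events of special interest, serious or not and reportable within one business day, "Hepatitis/transaminase increases", "Nephritis/Blood creatinine increases" and "Pancreatitis/ serum lipase and amylase increases".

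**What is measured.** The Section 7 calendar schedules "Amylase and Lipase", the blood count and the metabolic profile (which covers creatinine, AST, ALT, bilirubin and alkaline phosphatase) at screening and on Day 1 of Cycles 1 to 7. The blood count and metabolic profile are repeated at the safety visit and in follow-up.

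**The concern.** CTCAE grades for these tests can be computed from measured values; Appendix 1 itself prints the AST/ALT, bilirubin and creatinine grades as numeric cut-offs. Entry to the toxicity table, however, depends on whether a value caused symptoms, was treated or led to more tests, and on which section a site applies. An abnormality that holds a dose can then be absent from the reported rate. If that happens, the trial describes only part of a known class of harm. The stopping rule and the monitoring committee's adverse event summary draw on the same records, so they share the gap.

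**Working it through.** The plan states no figure for this point, so there is none to reproduce. The check is a comparison of sections, a count, and one illustration.

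**Step 1. The same finding under each section.** Management is taken from Appendix 1 as printed, only to see which recording rule applies.

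| Finding, no symptoms | Appendix 1 | Collected under 11.2.1? | Adverse event under 11.1.1? | Named in 11.1.3? |
|---|---|---|---|---|
| Grade ≥3 amylase or lipase | Hold and work-up; no treatment named in that note | No, if untreated | Yes, further tests | Yes |
| Grade 2 AST/ALT | Hold; LFTs rechecked about every 1 to 2 days; steroids if it persists beyond 3 to 5 days or worsens | No, if it settles untreated | Yes, further tests | Yes |
| Grade 2 creatinine | Hold; rechecked every 2 to 3 days; steroids if it persists or worsens | No, if it settles untreated | Yes, further tests | Yes |
| Grade 3 AST/ALT | Prompt IV steroid | Yes, treated | Yes | Yes |
| Grade 3 creatinine | Prompt steroid | Yes, treated | Yes | Yes |

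The first three rows give opposite answers under 11.2.1 and 11.1.1. Section 11.1.3 does not settle the matter. It describes an event of special interest as a kind of adverse event, and nothing says that such a report enters the 12.6.2 tables when 11.2.1 would leave the finding out. Blood-count changes that are neither symptomatic nor treated fall under the same 11.2.1 rule.

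**Step 2. Values with no planned summary.** Inputs are 28 subjects (Section 12.3) and 7 Day 1 draws (Section 7). Calendar footnote 16 has LFTs, electrolytes and creatinine reviewed before dosing, so the Cycle 1 Day 1 set is pre-dose; I assume amylase and lipase are drawn with it.

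- Post-first-dose Day 1 sets: 28 × (7 − 1) = 168.
- Amylase and lipase values: 168 × 2 = 336.

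This is a ceiling. It assumes that all 28 subjects reach Cycle 7, and it leaves out re-treatment, safety-visit and follow-up samples.

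**Step 3. Why a baseline is needed.** Section 3.1 admits AST or ALT up to 5 × ULN with hepatic metastases. Appendix 1 calls values above 3 and up to 5 × ULN Grade 2. A subject can therefore enter at Grade 2, and a worst-grade count alone would not separate this from change on treatment.

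**Step 4. Reach into Section 12.7 (illustration only).** Let p be the true proportion of subjects with a treatment-related Grade ≥3 event, and s the share of those subjects whose only such event is an uncollected laboratory value. The recorded rate is p(1 − s). The exact probability of ever reaching the printed limits (5 of 6, 8 of 12, 10 of 18, 13 of 24) is:

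| p | s = 0 | s = 10% | s = 20% | s = 30% |
|---|---|---|---|---|
| 40% | 0.19 | 0.10 | 0.05 | 0.02 |
| 50% | 0.51 | 0.33 | 0.19 | 0.09 |

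For example, p = 50% and s = 20% give a recorded rate of 0.50 × 0.80 = 0.40, and the chance of stopping falls from 0.51 to 0.19. The documents give no value for s. As a separate matter, the exact 95% lower limits for 10 of 18 and 13 of 24 are 30.8% and 32.8%, so the worded 33% criterion needs 11 and 14. With those limits the same comparison is 0.38 to 0.12.

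**The case against.** The strongest reply is that the protocol already catches most of these values. Section 11.1.1 makes a value that needs further tests an adverse event, and Appendix 1 asks for rechecks or a work-up in each doubtful row of Step 1. Section 11.1.3 requires prompt reporting of exactly these increases. Section 6 evaluates adverse events of all grades and those that interrupt the drug, and Section 6.2 requires dose modifications to be documented with reasons. This stands as far as it goes: at sites that follow 11.1.1 and 11.1.3, little would be lost. It does not remove the conflict with 11.2.1, and a note explaining a held dose is not a toxicity rate.

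A reader might also infer more than the documents support:

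- *That the frequency table is the only planned safety analysis.* Section 12.7 is a second one, though it uses the same records.
- *That laboratory toxicity is removed and its rates are biased low.* The sections conflict; they do not establish a settled removal. Understatement is possible, and its size is unknown.
- *That Grade 3 transaminase or creatinine rises disappear.* Appendix 1 calls for prompt steroids, so 11.2.1 would not leave them out. That guidance applies to events judged drug-related, which is also the class that Section 12.7 counts.
- *That results could not be compared with other reports.* The documents do not show that any comparator grades laboratory values separately, and the benchmark of about 30% in Section 12.7 is an adverse event rate.

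Finally, safety is a descriptive secondary objective in a single-arm trial of 28 subjects, and the response-rate decision is untouched. That is a fair limit on the weight of the point.

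**Conclusion.** The point holds in a limited form. Whether a laboratory abnormality is counted can depend on which of three sections a site applies, and no planned table uses the measured values, which would be immune to that choice. Laboratory-defined toxicity rates may be understated. The clearest exposure is asymptomatic Grade 3 or higher amylase or lipase; next come Grade 2 transaminase or creatinine rises that settle untreated, and untreated blood-count changes. The documents cannot fix the number of subjects affected. What can be counted is the unused information: at most 168 Day 1 sets, or 336 amylase and lipase values, if all 28 subjects complete seven cycles. The stopping-rule figures show direction and sensitivity under assumed values of s and are not an estimate. This is a cheap improvement and does not affect the primary analysis.

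**What to change.** 1. Reconcile Sections 11.1.1, 11.1.3 and 11.2.1 so that one stated rule decides when a laboratory value is recorded as an adverse event, and say whether reports of special interest enter the Section 12.6.2 tables. The management rules in Appendix 1 need no change for this.
2. Add to Section 12.6.2, for the safety population, a table of worst post-baseline CTCAE v4.03 grade computed from the laboratory values, whatever was reported as an adverse event. Cover AST, ALT, bilirubin, alkaline phosphatase, creatinine, amylase, lipase, ANC, hemoglobin and platelets. Present it as a shift from baseline grade (last value before the first dose), show initial treatment and re-treatment separately, and place it next to the adverse event table.
3. State in Section 12.7 whether a treatment-related Grade 3 or higher laboratory value with no symptoms or treatment counts towards the stopping rule.

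The cost is a short paragraph in each section and a few programmed tables, with no new tests or visits. Sections 14.1 and 14.2 say that only select data enter the EDC system, so the sponsor should confirm that the values and each laboratory's reference limits are captured; some added data entry may be needed. Reported laboratory toxicity may also look less favourable.

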### 12.6.3 Analysis Plans for Exploratory Objectives

To explore the relationship between PD-L1 expression and response to treatment, Fisher's exact test will be used. To explore the relationship between molecular subtype of bladder cancer and response to treatment, frequency tables will be constructed and Fisher's exact test will be used. To explore the relationship between genomic alterations, including mutational load, and changes in circulating immune biomarkers and response to treatment both Fisher's exact test and T-test will be used. Exploratory analyses correlating clinical outcomes and adverse events with stool microbiome diversity/composition as well as assessment of metabolomics and metagenomic whole genome sequencing may also be performed.

## 12.7 Interim Analysis/Criteria for Stopping Study

Though there has been limited experience with single agent CTLA-4 blockade in metastatic urothelial cancer, prior studies exploring combination PD-1/PD-L1 plus CTLA-4 blockade in metastatic urothelial cancer have reported a treatment-related Grade  $\geq 3$  adverse event rate of approximately 30%. A stopping rule for excessive toxicity will be employed after 6, 12, 18, and 24 subjects finish at least one cycle of treatment. This safety stopping rule will be performed with respect to all treatment-related Grade  $\geq 3$  adverse events. Two-sided 95% exact binomial confidence intervals (CIs) of these treatment-related Grade  $\geq 3$  adverse event rates will be constructed. If their lower bounds exceed 33%, the study drug will be considered unacceptably toxic for this patient population and enrollment will be halted. This corresponds to  $\geq 5$  out of 6 patients with grade  $\geq 3$  adverse events,  $\geq 8$  out of 12 patients with grade  $\geq 3$  adverse events,  $\geq 10$  out of 18 patients with grade  $\geq 3$  adverse events, and  $\geq 13$  out of 24 subjects with grade  $\geq 3$  adverse events.

There is a possibility of stopping at the 1st stage if no patients respond to treatment. In addition, the study accrual may be suspended in the case when none of the first 17 patients respond and

the decision to move onto the 2nd stage hinges on the response of the 18th patient. Otherwise, during these safety analyses, enrollment will continue.

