##### **6.1 Infusion Reactions**

In the event of a  $\leq$  Grade 2 infusion-related reaction, the infusion rate of study drug may be decreased by 50% or interrupted until resolution of the event and re-initiated at 50% of the initial rate until completion of the infusion. For subjects with a  $\leq$  Grade 2 infusion-related reaction, subsequent infusions may be administered at 50% of the initial rate. Acetaminophen and/or an antihistamine (eg, diphenhydramine) or equivalent medications per institutional standard may be administered at the discretion of the site investigator. If the infusion-related reaction is  $\geq$  Grade 3 or higher in severity, study drug will be discontinued. For management of subjects who experience an infusion reaction, please refer to the toxicity and management guidelines in Appendix 1.

As with any antibody, allergic reactions to dose administration are possible. Appropriate drugs and medical equipment to treat acute anaphylactic reactions must be immediately available, and study personnel must be trained to recognize and treat anaphylaxis. The study site must have immediate access to emergency resuscitation teams and equipment in addition to the ability to admit subjects to an intensive care unit if necessary.

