### 12.3 Sample Size and Accrual

A Simon's 2-stage design will be applied. Patients who do not receive drug or who do not complete 1 cycle of therapy for non-treatment related causes (eg, traffic accidents, trauma etc) will be replaced.

The null hypothesis that the true response rate is 2% will be tested against a one-sided alternative. In the first stage, 18 subjects will be accrued. If there are 0 responses in these 18 subjects, enrollment will be stopped. Otherwise, 10 additional subjects will be accrued for a total of 28. The null hypothesis will be rejected if 3 or more responses are observed in 28 subjects. This design yields a type I error rate of 0.02 and power of 80% when the true response rate is 15% or larger.

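### Section 12.7 times its toxicity looks by cycle finishers and prints boundaries only for those numbers, which does not fit the all-dosed safety population of 12.4 and can change a halt decision

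*Combined protocol and SAP*

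**What the plan says.** Section 12.7 fixes when the rule is applied: "A stopping rule for excessive toxicity will be employed after 6, 12, 18, and 24 subjects finish at least one cycle of treatment". It describes the event without restricting it to finishers: "This safety stopping rule will be performed with respect to all treatment-related Grade" ≥3 adverse events. The criterion is a two-sided 95% exact binomial interval: "If their lower bounds exceed 33%, the study drug will be considered unacceptably toxic for this patient population and enrollment will be halted". The section then translates this into counts, beginning with at least 5 "out of 6 patients with grade" ≥3 events, followed by at least 8 of 12, 10 of 18 and 13 of 24. It gives no boundary for any other denominator, does not name its analysis population, and does not define what finishing a cycle means. Enrollment continues during the safety analyses.

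Section 12.4 defines the safety population as "any patients that receive at least one dose of tremelimumab and will be used in the assessment of toxicity", with evaluability from first dose. Section 12.6.2 repeats that one dose makes a subject evaluable for toxicity.

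Sections 5, 12.3 and 12.5 replace subjects who receive no drug or who "do not complete 1 cycle of therapy for non-treatment related causes". Treatment-related exits are not replaced. Section 6.1 says that if an infusion reaction is Grade 3 "or higher in severity, study drug will be discontinued", and 6.4 repeats this, so an exit at the first infusion is a foreseen event.

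**The concern.** The trigger and the printed denominators are the same four numbers, so a data manager who follows 12.7 literally would tabulate events among cycle finishers. A subject who dies or is taken off in Cycle 1 by a treatment-related Grade ≥3 event may then appear in neither numerator nor denominator, although 12.4 puts that subject in the toxicity assessment. If early leavers are counted, the denominators at the looks become 7, 8, 14 and so on, and the printed counts no longer apply.

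At stake is whether enrollment halts for harm. A count restricted to those who tolerated Cycle 1 understates the event rate most when early toxicity is worst. Whichever subjects are counted, each toxic exit pushes the next look back while enrollment continues.

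**Working it through.** **Inputs.** Looks at 6, 12, 18 and 24 finishers, the printed boundaries, and the 33% criterion (12.7); 28 subjects in total (12.3); every dosed subject evaluable for toxicity (12.4, 12.6.2). The documents give no rate of Cycle 1 exits for treatment-related Grade ≥3 events. I assume shares s = 2%, 5%, 10% and 16% of all subjects. The 16% borrows the pooled monotherapy figure in 10.1.4, which is any AE leading to discontinuation at any time; it is a high scenario, not an estimate for Cycle 1.

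**Step 1: the plan's own boundaries.** The exact lower limit for x events in n subjects is the 2.5% quantile of Beta(x, n − x + 1).

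| Printed boundary | Lower limit | Above 33%? | Smallest count above 33% |
|---|---|---|---|
| 5/6 | 35.9% | yes | 5 |
| 8/12 | 34.9% | yes | 8 |
| 10/18 | 30.8% | no | 11 (35.8%) |
| 13/24 | 32.8% | no | 14 (36.6%) |

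The first two reproduce and the last two do not. All four would match a 30% threshold, or a one-sided 95% bound above 33%. The documents do not say which was meant.

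**Step 2: the same data under the two counts.**

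- First look: 8 dosed, 2 taken off in Cycle 1 by treatment-related Grade ≥3 events, 4 events among the 6 finishers. Finishers only: 4/6, lower limit 22.3%, continue. All dosed: (4 + 2)/(6 + 2) = 6/8, lower limit 34.9%, halt.
- Second look: finishers 7/12, lower limit 27.7%, continue. With two such exits, 9/14, lower limit 35.1%, halt.
- Mixing the two also misleads: 4 events among 6 finishers plus one exit meets the printed count of 5, but 5/7 has a lower limit of 29.0%, below the criterion.

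**Step 3: loss of stopping power if only finishers count.** Let p be the true rate of treatment-related Grade ≥3 events among dosed subjects, with s contained in p. The rate among finishers is (p − s)/(1 − s). For p = 60% and s = 10% this is 0.50/0.90 = 55.6%; for s = 16%, 0.44/0.84 = 52.4%. Simulated chance of halting (28 dosed subjects, printed boundaries, at least 100,000 trials per scenario):

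| True rate | All dosed | s = 2% | s = 5% | s = 10% | s = 16% |
|---|---|---|---|---|---|
| 60% | 84% | 82% | 78% | 70% | 56% |
| 50% | 51% | 47% | 42% | 31% | 18% |

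**Step 4: finisher-triggered looks, all dosed subjects counted.** Applying the 33% bound to the actual denominator at p = 60%, the chance of halting is 75% to 79% over the same shares. The same criterion at exactly 6, 12, 18 and 24 dosed subjects (5/6, 8/12, 11/18, 14/24) gives about 73%. No stopping power is lost.

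**Step 5: delay.** In Step 2 the first look waits for the 8th dosed subject instead of the 6th. With five unreplaced Cycle 1 exits among 28, only 28 − 5 = 23 subjects finish a cycle, so the fourth look never occurs. In a trial that runs to 28, the probability is P(X ≥ 5), X ~ Binomial(28, s): about 1% at s = 5%, 14% at 10% and 47% at 16%.

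**The case against.** A reader might infer that the plan removes Cycle 1 toxicity exits from the counts and so will miss a needed halt. The documents do not support that. The words about finishing a cycle say when to look; the next sentence covers all treatment-related Grade ≥3 events; and 12.4 and 12.6.2 both point to all dosed subjects. The operative criterion is the lower bound, which works for any denominator, and the printed counts can be read as illustrations of it. On that reading Step 4 shows no loss of power.

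Two further points have force. A cycle is a single Day 1 infusion followed by the rest of 28 days (5.1), and subjects taken off drug are still followed, so a subject observed to Day 28 might be said to have finished Cycle 1 without a second dose. Also, SAEs reach the coordinating organization within one business day, and the DSMC receives AE summaries and stopping-rule data (11.2.2, 13.2), so early severe events would not go unseen.

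All of this limits the claim. It does not remove it: 12.7 names no population, the only boundaries it prints suit a finishers-only count, and expedited reporting does not replace a formal rule. The delay in Step 5 stays even when all dosed subjects are counted.

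**Conclusion.** Section 12.7 does not fit 12.4 and 12.6.2, and the mismatch can turn a halt into a continuation. This is an inconsistency about who is counted, not a stated exclusion.

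The power loss in Step 3 (2 to 28 percentage points at a true rate of 60%) arises only on a finishers-only count with the printed boundaries, and it rests on assumed exit shares. At a 2% share it is small. The 16% column should not be read as what the documents predict.

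What holds on either count is that looks are postponed by exits before a cycle is finished, that the fourth look is lost with five or more unreplaced exits among 28, and that the printed 10/18 and 13/24 do not meet the stated 33% criterion. Because the rule decides whether enrollment halts for harm and the correction is cheap, it should be made.

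**What to change.** In 12.7:

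- State that the stopping rule uses the 12.4 safety population: all dosed subjects, with no exceptions. A dosed subject replaced for response still counts for toxicity.
- Hold each look when the 6th, 12th, 18th and 24th dosed subject has either completed 28 days from first dose or left earlier.
- Count all treatment-related Grade ≥3 events to date in the dosed subjects, with numerator and denominator from the same subjects.
- Apply the stated interval criterion to the actual denominator, keeping any printed counts as examples.
- Reconcile 10/18 and 13/24 with the 33% criterion, so that threshold, interval and counts agree.

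The change takes a few sentences and no extra data, visits or patients. Compared with a finishers-only count, the population change raises the chance of a halt, including a false one, by an amount that depends on the Cycle 1 exit rate. For example, at a true rate of 33% with the printed boundaries it is about 6% counting all dosed subjects and 3% counting finishers only, if 16% of events end Cycle 1 early (0.33 × 0.16 = about 5% of subjects). The reconciliation also moves the result: at a true rate of 60%, counting all dosed subjects, the printed counts halt in about 84% of trials and the 33% criterion in about 73%. The operating characteristics should be restated once the sponsor has settled the criterion.
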